11.1.2 Secondary outcomes

Among all AIS patients (patient group A) for all three waves of CNSR: ([Table 3.1](#)

[figure not shown]
Proportion of 3h IV-rtPA treatment within 2h of symptom onset arrival and Proportion of 4.5 h IV-rtPA treatment within 3.5h of symptom onset arrival among Among all AIS patients)

[figure not shown]
[figure not shown]
- Proportion of patients who arrived at hospital within 2h of symptom onset and who received IV-rtPA treatment within 3h of symptom onset (patient group C);
- Proportion of patients who arrived at hospital within 3.5h of symptom onset and who received IV-rtPA treatment within 4.5h of symptom onset (patient group C');

[figure not shown]
Among 3h &4.5h IV-rtPA patients (patient group C) for all three waves of CNSR: ([Table 3.2](#)

DTN time, onset-to-door, onset-to-needle time and Proportion of DTN time less than 60 minutes among 3h & 4.5h IV-rtPA patients)

- The door-to-needle (DTN) time (time between arrival at hospital and the administration of IV-rtPA treatment);
- Proportion of patients DTN time \leq 60 minutes (min);
- Time between symptom onset and arrival at hospital;
- Time between symptom onset and the administration of IV-rtPA treatment.

11.3 SAFETY ANALYSIS

Not applicable.

12. QUALITY CONTROL

For the CNSR, safety and risk control were assessed by the Data Safety and Monitoring Board (DSMB) before the study. All hospitals participating in the CNSR were selected by a Steering Committee using a convenient sampling method from the China National Network of Stroke Research developed by the National Center of Quality Management in Stroke Care. Clinical research associates conducted data verification on site during the study. Data management team of NCRCND performed remote real time data supervision for all the data cleaning, integration, analysis, and other processing.

The internal data validity of CNSR I, II, and III were ensured by employing trained clinical research coordinators (CRCs) to guarantee the quality of data entry. Independent contract research organizations (CROs) were invited to monitor the study procedures and to ensure the quality of data entry. All data elements collected by PRF, web-based CRF, or EDC system were manually or mechanically checked for completeness, coding correctness, and appropriateness of the diagnostic algorithm. A professional data processing company was responsible for the computer or PAD data entry.

For this study, the standard operation procedures (SOPs) of Boehringer Ingelheim (BI), such as NIS SOP, will be strictly followed. In addition, key elements of the International Society for Pharmacoepidemiology Good Pharmacoepidemiology Practices (GPP) will be followed. The statistical analysis method will be reviewed and repeated by a second analyst. All the data cleaning, integration, analysis, and other processing will be conducted under the guidance and supervision of data management team of NCRCND. The study report will be reviewed, approved, and archived per SOPs of BI.

ANNEX 1. ADDITIONAL INFORMATION

1. DEFINITION OF VARIABLES

2. DICTIONARY OF VARIABLES

	Variable Name	Type	Label & Value
1	Wave	character	Study wave of CNSR 1 2 3
2	[REDACTED]	[REDACTED]	[REDACTED]
3	hosp_id	character	Hospital ID
4	[REDACTED]	[REDACTED]	[REDACTED]
5	hosp_name	character	Hospital Name
6	[REDACTED]	[REDACTED]	[REDACTED]
7	[REDACTED]	[REDACTED]	[REDACTED]
8	[REDACTED]	[REDACTED]	[REDACTED]
9	[REDACTED]	[REDACTED]	[REDACTED]
10	[REDACTED]	[REDACTED]	[REDACTED]
11	[REDACTED]	[REDACTED]	[REDACTED]
12	[REDACTED]	[REDACTED]	[REDACTED]
13	[REDACTED]	[REDACTED]	[REDACTED]
14	[REDACTED]	[REDACTED]	[REDACTED]
15	[REDACTED]	[REDACTED]	[REDACTED]
16	[REDACTED]	[REDACTED]	[REDACTED]
17	[REDACTED]	[REDACTED]	[REDACTED]
18	[REDACTED]	[REDACTED]	[REDACTED]
19	onset_arriv_hour	numerical	Hours From Onset To Hospital Arrival
20	arriv_tpa_hour	numerical	Hours From Hospital Arrival To Tpa Treatment
21	ONSET_TPA_ho ur	numerical	Hours From Onset To Tpa Treatment
22	TPA_AC	numerical	Absolute Contraindications For Tpa: 0=No;1=Yes

3、MOCK TABLE&FIGUREPrimary outcomes:

Table 1 Proportion of 3 h IV-rtPA treatment among 2h IVT eligible patients & 4.5h IV-rtPA treatment among 3.5h IVT eligible patients

Patients	ALL	CNSR1	CNSR2	CNSR3
3h IV-rtPA / 2h IVT eligible	n/N % (95%CI)	n/N % (95%CI)	n/N % (95%CI)	n/N % (95%CI)
4.5h IV-rtPA / 3.5h IVT eligible	n/N % (95%CI)	n/N % (95%CI)	n/N % (95%CI)	n/N % (95%CI)

Secondary outcomes:

Table 3.1 Proportion of 3h IV-rtPA and Proportion of 4.5 h IV-rtPA treatment among all AIS patients

Proportion	ALL	CNSR1	CNSR2	CNSR3
3h IV-rtPA /all AIS patients	n/N % (95%CI)	n/N % (95%CI)	n/N % (95%CI)	n/N % (95%CI)
4.5h IV-rtPA /all AIS patients	n/N % (95%CI)	n/N % (95%CI)	n/N % (95%CI)	n/N % (95%CI)

Table 3.2.1 DTN time, onset-to-door, onset-to-needle time and Proportion of DTN time less than 60 minutes among 3h IV-rtPA patients

	All N=	CNSR1 N=	CNSR2 N=	CNSR3 N=
DTN time (minutes)	Median(IQR) (MIN,MAX) Mean(SD)	Median(IQR) (MIN,MAX) Mean(SD)	Median(IQR) (MIN,MAX) Mean(SD)	Median(IQR) (MIN,MAX) Mean(SD)
DTN ≤ 60 minutes %	% (95%CI)	% (95%CI)	% (95%CI)	% (95%CI)
Onset-to-door (minutes)	Median(IQR) (MIN,MAX) Mean(SD)	Median(IQR) (MIN,MAX) Mean(SD)	Median(IQR) (MIN,MAX) Mean(SD)	Median(IQR) (MIN,MAX) Mean(SD)
Onset-to-needle time(minutes)	Median(IQR) (MIN,MAX) Mean(SD)	Median(IQR) (MIN,MAX) Mean(SD)	Median(IQR) (MIN,MAX) Mean(SD)	Median(IQR) (MIN,MAX) Mean(SD)

[figure not shown]
Table 3.2.2 DTN time, onset-to-door, onset-to-needle time and Proportion of DTN time less than 60 minutes among 4.5h IV-rtPA patients

[figure not shown]
	All N=	CNSR1 N=	CNSR2 N=	CNSR3 N=
DTN time (minutes)	Median(IQR) (MIN,MAX) Mean(SD)	Median(IQR) (MIN,MAX) Mean(SD)	Median(IQR) (MIN,MAX) Mean(SD)	Median(IQR) (MIN,MAX) Mean(SD)
DTN ≤ 60 minutes %	% (95%CI)	% (95%CI)	% (95%CI)	% (95%CI)
Onset-to-door (minutes)	Median(IQR) (MIN,MAX) Mean(SD)	Median(IQR) (MIN,MAX) Mean(SD)	Median(IQR) (MIN,MAX) Mean(SD)	Median(IQR) (MIN,MAX) Mean(SD)
Onset-to-needle time(minutes)	Median(IQR) (MIN,MAX) Mean(SD)	Median(IQR) (MIN,MAX) Mean(SD)	Median(IQR) (MIN,MAX) Mean(SD)	Median(IQR) (MIN,MAX) Mean(SD)

[REDACTED]

[REDACTED]

[REDACTED]

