Till 2017, three waves of CNSR were completed: 2007-2008 (CNSR I), 2012-2013 (CNSR II), and 2015-2017 (CNSR III). The number of hospitals participating each of CNSR were 132, 219, and 201, respectively. When compared to CNSR I, data from CNSR II showed a 1.17-fold increase in the adjusted odds of delivering evidence-based performance metrics for ischemic stroke (IS) care. Nevertheless, no statistically significant difference in the proportion of patient who received intravenous thrombolytics (IVT) treatment within 3 hours (h) of symptom onset was observed between the two CNSR [P20-03289].

In China, IV-rtPA was approved for the treatment of AIS patients within 3h of symptom onset without absolute contraindications. However, in 2008, the European Cooperative Acute Stroke Study (ECASS) III study concluded that AIS patients could still benefit from IV-rtPA treatment when given between 3h and 4.5h [P08-12177]. The Chinese treatment guideline for AIS was updated in 2010, for which a recommendation of IV-rtPA treatment within 3h to 4.5h of symptom onset was added [P20-03291].

The current study aims at evaluating differences, if any, in clinical practice of IV-rtPA treatment among AIS patients from 2007 to 2017. In addition, the study will also provide information on the demographic and clinical characteristics of AIS patients receiving IV-rtPA in China. Taken together, the study will help us to better understand the trend of clinical practices for AIS treatment in China during the last decade, especially after the update of the

national AIS treatment guideline and the continuous efforts made by academic society and MOH in the field of stroke care.

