## **8. RESEARCH QUESTION AND OBJECTIVES**

The present study is to be conducted based on the AIS patient data collected from CNSR I, II, and III.

The primary objectives are:

- To investigate the temporal changes in the proportion of IV-rtPA treatment from 2007 to 2017 among IVT-eligible patients (patient groups B and B') and overall AIS patients (patient group A) in China;
- To investigate the temporal changes in IV-rtPA treatment time intervals from 2007 to 2017 among IV-rtPA-treated patients (patient groups C and C') in China.

The secondary objectives are:

- To describe the demographic and clinical characteristics of the IV-rtPA-treated patients (patient groups C and C'), IVT-eligible patients (patient groups B and B') and the overall AIS patients (patient group A) from 2007 to 2017 from the CNSR I to III.

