## 9.5 STUDY SIZE

It was estimated that in CNSR I, II, and III, the number of total AIS patients is 14704, 19604, and 15204, respectively.

Assuming the IV-rtPA-treated among IVT-eligible patients in CNSR I, II, and III are 4%, 5%, and 28% with the 95% confidence interval (CI) for each wave as below, then which can be distinguished with current study size.

CNSR	I	II	III
Assumed IV-rtPA proportion among eligible patients % (95% CI)	4% (3.7-4.3%)	5% (4.7-5.3%)	28% (27.3-28.7%)

No formal sample size calculation is performed due to the nature of this study. All eligible AIS patients within the existing database from the three waves of CNSR will be included in this study.

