6. RESEARCH QUESTION AND OBJECTIVE

Research Question:

Whether the quality of IV-rtPA treatment thrombolysis treatment has been improved with the continuous development of stroke centers and stroke care quality control networks supported by academic society and MOH during the last decade in China?

Primary Objectives:

- To investigate the temporal changes in the proportion of IV-rtPA treatment from 2007 to 2017 among intravenous thrombolytics (IVT) eligible patients and overall AIS patients in China;
- To investigate the temporal changes in IV-rtPA treatment time intervals from 2007 to 2017 among IV-rtPA treated patients in China.

Secondary Objectives:

- To describe the demographic and clinical characteristics of the IV-rtPA treated patients, IVT eligible patients and the overall AIS patients from the CNSR I to III.

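### Both primary objectives concern change over time, but the visible main analysis and its table shells give no between-wave difference and no confidence interval for any time interval

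*SAP*

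**What the plan says.** Protocol section 8 sets as a primary objective "To investigate the temporal changes in the proportion of IV-rtPA treatment from 2007 to 2017", among IVT-eligible and all AIS patients. SAP section 6 repeats this and adds a second primary objective: "To investigate the temporal changes in IV-rtPA treatment time intervals from 2007 to 2017 among IV-rtPA treated patients in China". Protocol section 7 describes the aim in the same spirit: "The current study aims at evaluating differences, if any, in clinical practice of IV-rtPA treatment among AIS patients from 2007 to 2017". The SAP's research question is "Whether the quality of IV-rtPA treatment thrombolysis treatment has been improved".

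The visible methods (protocol 9.7.1; SAP 11 and 11.1) offer summary statistics for continuous data, and frequencies and proportions with 95% CIs for categorical data. Both documents call the study descriptive. SAP 11.1.1 and 11.1.2 send the outcomes to these shells in SAP Annex 1:

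- "Table 1 Proportion of 3 h IV-rtPA treatment among 2h IVT eligible patients & 4.5h IV-rtPA treatment among 3.5h IVT eligible patients", and Table 3.1 for all AIS patients: columns ALL, CNSR1, CNSR2 and CNSR3, each with n/N and a percentage with 95% CI.
- "Table 3.2.1 DTN time, onset-to-door, onset-to-needle time and Proportion of DTN time less than 60 minutes among 3h IV-rtPA patients", and its 4.5h counterpart, Table 3.2.2: the same four columns. The three time intervals have median, IQR, minimum, maximum, mean and SD. Only the share with DTN of 60 minutes or less has a CI.

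Protocol 9.5 assumes treated proportions of 4%, 5% and 28% among eligible patients, prints a 95% CI for each wave, and concludes "then which can be distinguished with current study size".

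**The concern.** The quantity named in the objectives is a contrast between waves, but the visible outputs are separate levels for each wave. A reader must construct the change from them.

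For proportions, the only visible hint of how waves are to be told apart is the set of separate CIs in protocol 9.5. Comparing separate CIs is stricter than examining the CI of the difference, so a modest change can look like no change. Wave I against II is where this could matter: protocol section 7 reports that earlier work found no significant difference between these waves in thrombolysis within 3h, whereas 9.5 expects 4% and 5% to be separable.

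For the time intervals the gap is wider, because the shells give no CI even for a single wave. Wave I may also be small. With 4% treated, 14704 patients and an assumed 10–30% eligible, group C would have 0.04 × 14704 × 0.10 = 59 to 0.04 × 14704 × 0.30 = 176 patients.

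**Working it through.** **Inputs.** Proportions of 4%, 5% and 28% (protocol 9.5). All-AIS totals of 14704, 19604 and 15204 (protocol 9.5); the SAP study-population text gives 12415 for wave I. The number of eligible patients is not stated, so the eligible share f is an assumption, taken as equal in all waves. Clustering is ignored until step 5.

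**1. The protocol's own CIs.** Formula: p ± 1.96·√(p(1−p)/n), with n the all-AIS total.
- I: 4% → 3.68–4.32 (stated 3.7–4.3); with 12415, 3.66–4.34
- II: 5% → 4.69–5.31 (stated 4.7–5.3)
- III: 28% → 27.29–28.71 (stated 27.3–28.7)

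These match, but the label says eligible patients while n is all AIS patients. Working back from the rounded half-widths (at most 0.35, 0.35 and 0.75 points), n must be at least 12042, 14895 and 13768, which is 82%, 76% and 91% of the protocol totals. The printed precision therefore needs nearly everyone to be eligible.

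**2. Separate CIs against the CI of the difference, II−I.** With n₁ = f·14704 (or f·12415) and n₂ = f·19604, the difference is 1.0 ± 100·1.96·√(0.04·0.96/n₁ + 0.05·0.95/n₂) points.

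| Wave I total | f | CI wave I | CI wave II | Overlap | II−I (points) |
|---|---|---|---|---|---|
| 14704 | 100% | 3.68–4.32 | 4.69–5.31 | no | 0.56 to 1.44 |
| 14704 | 40% | 3.50–4.50 | 4.52–5.48 | no | 0.30 to 1.70 |
| 14704 | 30% | 3.42–4.58 | 4.44–5.56 | yes | 0.20 to 1.80 |
| 14704 | 20% | 3.29–4.71 | 4.32–5.68 | yes | 0.02 to 1.98 |
| 14704 | 10% | 3.00–5.00 | 4.04–5.96 | yes | −0.39 to 2.39 |
| 12415 | 40% | 3.45–4.55 | 4.52–5.48 | yes | 0.27 to 1.73 |
| 12415 | 30% | 3.37–4.63 | 4.44–5.56 | yes | 0.16 to 1.84 |
| 12415 | 20% | 3.23–4.77 | 4.32–5.68 | yes | −0.03 to 2.03 |
| 12415 | 10% | 2.91–5.09 | 4.04–5.96 | yes | −0.46 to 2.46 |

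**3. Where the two readings disagree.** The separate CIs part only from f ≈ 39% (42% with 12415). The CI of the difference excludes zero from f ≈ 19% (21%), and a pooled z test reaches 0.05 from f ≈ 20% (22%). Taking the stricter lower limit, they disagree at about 20–39%, or 22–42% with 12415. At these sizes, non-overlap requires |z| > 2.76, a two-sided error near 0.006.

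**4. Wave III.** Even at f = 5%, III−II is 23.0 points (19.5 to 26.5) and III−I is 24.0 points (20.5 to 27.5).

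**5. Clustering.** A design effect D multiplies the half-width by √D. At f = 30% the II−I interval reaches zero when D = (1.0/0.803)² = 1.55, or (1.0/0.841)² = 1.41 with 12415. Eligible patients per hospital would average (4411 + 5881)/(132 + 219) ≈ 29. Taking D = 1 + (29 − 1)·ICC, an intracluster correlation of about 0.02 gives 1.55.

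**6. ALL column.** At equal eligible shares, (0.04·14704 + 0.05·19604 + 0.28·15204)/49512 = 11.8%, a level that none of the three waves has.

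**The case against.** A reader might infer that the plan judges change by whether CIs overlap. The documents do not say so. No analysis section sets a decision rule, and protocol 9.5 is a study-size section that also disclaims any formal calculation. It never mentions overlap and concerns proportions only.

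A reader might also infer that no contrast is planned anywhere. That cannot be established. Text is blacked out in the abstract's data-analysis entry, after protocol 9.7.1 and after SAP Table 3.2.2. No SAP section 11.2 or Table 2 is visible, and the secondary objective on patient characteristics has no visible shell, so the visible outputs are incomplete. This limits the point to SAP 11.1 and the tables it cites.

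It is fair to add that the shells allow some repair. With n/N, anyone can compute an unclustered difference in proportions. With N, mean and SD, an approximate unclustered CI for a difference in means is possible. Neither a clustered CI nor a CI for a difference in medians can be recovered from those summaries.

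The numerical illustration is also fragile. It rests on an assumed eligible share, the 20% case crosses zero with the SAP's wave I total, and modest clustering removes the 30% case. The proposed change could therefore show an uncertain I-to-II change, which would still be an accurate report.

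The descriptive label is a weaker defence: a difference with a CI is itself descriptive. An ALL column is ordinary in such tables, and keeping it does no harm beside the wave columns.

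**Conclusion.** The point holds for the visible main analysis. Both primary objectives ask for change, and the outputs assigned to them show none. The interval outcomes lack even a per-wave CI, apart from the proportion with DTN of 60 minutes or less.

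The practical effect is confined mainly to wave I against II. At assumed eligible shares of about 20–39% (22–42% with 12415), without clustering, the choice between separate CIs and the CI of the difference alters the reading of 4% against 5%. At 10% the difference is not resolved either way, and at 30% a design effect above about 1.4–1.55 leaves it unresolved. The rise to wave III is clear at every share tried, so the documents do not support a claim that the study would miss the main trend.

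The protocol's statement that 4% and 5% are separable rests on all-AIS denominators and is not shown for eligible patients. The change should be made, but the study does not fail without it.

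**What to change.** - In Tables 1, 3.1, 3.2.1 and 3.2.2, add II−I, III−II and III−I, each with a 95% CI: differences in proportions for the binary outcomes and differences in medians for the three time intervals. No p-values are needed. Keeping the ALL column is optional.
- State in SAP 11.1 that these CIs use a hospital-level bootstrap or a cluster-robust variance by hosp_id, which is already in the variable dictionary. The wave counts sum to 132 + 219 + 201 = 552 against 491 hospitals in protocol 9.6. If 491 counts distinct hospitals, some took part in more than one wave, so the identifier should be consistent across waves and the method should keep a hospital's waves together.
- Restate the closing claim of protocol 9.5 as the expected CI for the difference among eligible patients, over a stated range of eligible shares, and reconcile 14704 with 12415 for wave I.
- If a redacted section already defines a between-wave contrast, cite it in SAP 11.1 and report it in these tables.

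The cost is three columns per table, a sentence or two in the SAP and a revised sentence in protocol 9.5. No new data are needed. The tables become slightly larger, and the I-to-II change may be shown as uncertain.

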**3) IV-rtPA-treated patients (patient groups C and C')**

1. Inclusion criteria:

- (1) Met the in- and exclusion criteria of "IVT-eligible patients"
- (2) Treated with IV-rtPA within 3h (patient group C) or 4.5h (patient group C') of symptom onset

2. Exclusion criteria:

- (1) Not received IVT
- (2) Received IVT other than rtPA
- (3) Treated with IV-rtPA after 3h (patient group C) or 4.5h (patient group C') of symptom onset
- (4) Received additional treatments with intra-arterial reperfusion or experimental therapies

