#### 9.3.2.2 Secondary outcomes: the analysis will be performed for each wave of CNSR

Among all AIS patients (patient group A), the following secondary outcomes will be assessed:

[figure not shown]
- Proportion of patients who arrived at hospital within 2h of symptom onset and who received IV-rtPA treatment within 3h of symptom onset (patient group C);
- Proportion of patients who arrived at hospital within 3.5h of symptom onset and who received IV-rtPA treatment within 4.5h of symptom onset (patient group C');

Among 3h IV-rtPA-treated patients (patient group C), the following secondary outcomes will be assessed

- The door-to-needle (DTN) time (time between arrival at hospital and the administration of IV-rtPA treatment);
- Proportion of patients DTN time  $\leq$  60 minutes (min);
- Time between symptom onset and arrival at hospital;
- Time between symptom onset and the administration of IV-rtPA treatment.

Among 4.5h IV-rtPA-treated patients (patient group C'), the following secondary outcomes will be assessed

- The DTN time;
- Proportion of patients DTN time  $\leq$  60 min;
- Time between symptom onset and arrival at hospital;
- Time between symptom onset and the administration of IV-rtPA treatment.

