8.2.2 Secondary outcomes

Among all AIS patients (patient group A) for all three waves of CNSR:

- Proportion of patients who arrived at hospital within 2h of symptom onset and who received IV-rtPA treatment within 3h of symptom onset (patient group C);
- Proportion of patients who arrived at hospital within 3.5h of symptom onset and who received IV-rtPA treatment within 4.5h of symptom onset (patient group C');

[figure not shown]
[figure not shown]
Among 3h IV-rtPA patients (patient group C) for all three waves of CNSR:

- The door-to-needle (DTN) time (time between arrival at hospital and the administration of IV-rtPA treatment);
- Proportion of patients DTN time \leq 60 minutes (min);
- Time between symptom onset and arrival at hospital;
- Time between symptom onset and the administration of IV-rtPA treatment.

Among 4.5h IV-rtPA patients (patient group C') for all three waves of CNSR:

- The DTN time;

- Proportion of patients DTN time \leq 60 min;
- Time between symptom onset and arrival at hospital;
- Time between symptom onset and the administration of IV-rtPA treatment.

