11.1 MAIN ANALYSIS

Patient group A includes patients aged 18-80 years and diagnosed with AIS on admission. Patients with missing baseline data including age and gender and diagnosed with intracranial hemorrhage (ICH), Transient Ischemic Attack (TIA), subarachnoid hemorrhage (SAH), or unspecific stroke and arrived at hospital after 7 days of symptom onset will be excluded.

Patient group B and patient group B' are both based on patient group A. And patients with missing key data will be excluded from patient group B and patient group B', including symptom onset time or last known well time, hospital arrival time, whether received IVT treatment or not and the time of IVT treatment.

Patients documented with IVT absolute contraindications, according to the case report form (CRF) for each of CNSR will be also excluded from patient group B and patient group B'.

Patients group B included patients who arrived at hospital within 2h of symptom onset.

[figure not shown]
Patients group B' included patients who arrived at hospital within 3.5h of symptom onset.

Patient group C is based on patients group B and patient group C' is based patient group B'. And both patient group C and patients group C' are to meet the inclusion criteria of "IVT-eligible patients". Patients not received IVT or received IVT other than rtPA or received additional treatments with intra-arterial reperfusion or experimental therapies will be excluded. Patients group C included patients who were treated with IV-rtPA within 3h. Patients group C' included patients who were treated with IV-rtPA within 4.5h.

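### The all-AIS treatment proportion uses a numerator limited to early-arriving, IVT-eligible patients, so it omits some in-window treatments and modestly understates a rise as door-to-needle time shortens

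*SAP*

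**What the plan says.** SAP section 6 states the objective as "To investigate the temporal changes in the proportion of IV-rtPA treatment from 2007 to 2017 among intravenous thrombolytics (IVT) eligible patients and overall AIS patients"; Protocol section 8 agrees. For overall AIS patients it sets no arrival limit.

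The outcome serving that part is secondary. Protocol 9.3.2.2 defines the 3h version as "Proportion of patients who arrived at hospital within 2h of symptom onset and who received IV-rtPA treatment within 3h of symptom onset", identified as group C and taken among group A. The 4.5h version uses 3.5h, 4.5h and group C'. SAP 8.2.2 and 11.1.2 repeat both.

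C is a subset of B, and C' of B' (Protocol 9.2; SAP 7.2 and 11.1). C and C' therefore inherit the arrival limit and the exclusion for documented absolute contraindications. They also drop patients with added intra-arterial or experimental therapy. Group A takes AIS patients aged 18-80 who arrived within 7 days.

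SAP 11.1.2 includes the arrival limit when it names Table 3.1. In the mock Table 3.1 of SAP Annex 1, neither the title nor the row labels do; the 3h row reads "3h IV-rtPA /all AIS patients".

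**The concern.** A one-hour gap between arrival limit and treatment limit suits C/B and C'/B', where it defines who could reasonably be treated in time. It has no such role when the denominator is every AIS patient arriving within a week. There, a treated patient outside the limit is simply counted as untreated.

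This matters because the study measures a trend. SAP section 6 asks whether treatment quality improved, and DTN is followed by wave. If the numerator misses more patients as hospitals become faster, the all-AIS proportion understates part of the improvement under study. A reader of Table 3.1 alone would also take its rows as unrestricted treatment rates.

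**Working it through.** **Plan figures.** The plan gives no expected value for the all-AIS proportion. Its only numerical precision statement (Protocol 9.5) concerns eligible patients. It reproduces as p ± 1.96·√(p(1−p)/N) with the all-AIS N of 14704, 19604 and 15204: 3.68-4.32%, 4.69-5.31% and 27.29-28.71%, against the stated 3.7-4.3%, 4.7-5.3% and 27.3-28.7%. Nothing below depends on it.

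**Step 1: who is lost.** These cases follow from the definitions alone.

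| Group A patient | 3h row | 4.5h row |
|---|---|---|
| Arrives 150 min, treated 175 min, eligible | not counted | counted |
| Arrives 220 min, treated 260 min, eligible | outside window | not counted |
| Arrives early, treated in-window despite a documented contraindication | not counted | not counted |

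**Step 2: direction.** Let W be the treatment limit and A the arrival limit, in minutes: (180, 120) or (270, 210). Someone arriving at t > A and treated by W has DTN ≤ W − t < W − A = 60 min. The arrival rule thus removes only treatments with DTN under 60 min. With arrival density f and DTN distribution F,

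number lost ∝ ∫ from A to W of f(t)·F(W − t) dt.

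If f and the decision to treat stay fixed and DTN shortens, F(W − t) cannot fall at any t, so the number lost cannot fall. It is zero if no DTN is under 60 min.

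**Step 3: size.** The documents contain no DTN or arrival distribution. Assumptions: DTN log-normal with log-SD 0.4 and independent of arrival; arrivals over (0, W) early-weighted (Beta(1,2)), uniform, or late-weighted (Beta(2,1)).

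Share lost = lost / (kept + lost). For the 3h row with uniform arrivals and a median of 60 min, per 100 arrivals in the window: 4.22 / (59.71 + 4.22) = 6.6%.

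Share of in-window treated patients lost (simulation, 1,000,000 arrivals per scenario; direct integration agrees to within about 0.1 point):

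| Row, arrivals | Median DTN 120 | 80 | 60 | 45 | 30 min |
|---|---|---|---|---|---|
| 3h, early | 0.2% | 1.2% | 2.7% | 4.9% | 7.8% |
| 3h, uniform | 0.6% | 2.9% | 6.6% | 11.7% | 19.0% |
| 3h, late | 1.8% | 7.1% | 14.3% | 23.2% | 34.8% |
| 4.5h, early | 0.1% | 0.4% | 1.1% | 2.1% | 3.4% |
| 4.5h, uniform | 0.2% | 1.5% | 3.7% | 6.9% | 11.7% |
| 4.5h, late | 0.7% | 3.5% | 7.9% | 13.9% | 22.5% |

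The share rises at every step to a shorter DTN in all six scenarios.

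**Step 4: effect on a trend.** Under uniform arrivals the 3h loss is 0.9% at a median of 110 min, 6.6% at 60 and 11.7% at 45. If the median fell from 110 to 60 min, the wave-to-wave ratio would be multiplied by (1 − 0.066)/(1 − 0.009) = 0.942, about 6% too low. From 110 to 45 it would be (1 − 0.117)/(1 − 0.009) = 0.891, about 11% too low. For the 4.5h row (0.4%, 3.7%, 6.9%) the factors are 0.963/0.996 = 0.967 and 0.931/0.996 = 0.935.

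The documents give nothing from which to size the loss of patients treated despite a contraindication.

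**The case against.** **The limit is declared.** This stands. The outcome text in both documents gives it, and so does the SAP 11.1.2 name for Table 3.1. Only the Annex 1 title and labels lack it. Declaring it does not make C/A the treatment proportion that the objective names.

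**The 4.5h row recovers many of them.** This also stands. An eligible patient arriving between 2h and 3h and treated by 3h is missing from the 3h row but counts in the 4.5h row. Through the arrival rule, the 4.5h row loses only arrivals between 3.5h and 4.5h.

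**The size is assumed.** True. Growth across waves also needs similar arrival patterns and treatment decisions. The effect attenuates a rise and does not create one. The plan assumes 4% to 28% among eligible patients; a relative loss of a few percent would not hide a change of that order in the all-AIS figure.

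**Redacted text may already hold such a row.** Possible: parts of the outcome and analysis text are blacked out. The point is limited to what can be read.

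**A stronger reading about DTN.** Because the arrival rule removes only fast treatments, a reader might infer that group C also understates the share with DTN ≤ 60 min and its change. That does not follow. Late arrivals enter the in-window treated set only if they were treated fast, while slower treatments of the same arrivals fall outside the window. Adding them selects on the outcome. In the uniform-arrival model with the 3h window:

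| Median DTN | All arrivals | Group C | All in-window treated |
|---|---|---|---|
| 110 min | 6.5% | 12.0% | 12.8% |
| 60 min | 50.0% | 55.8% | 58.7% |
| 45 min | 76.4% | 79.1% | 81.6% |

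C is closer to the underlying share each time. The one-hour gap therefore has a purpose in Tables 3.2.1 and 3.2.2.

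**Conclusion.** The point holds for the all-AIS proportion. C/A and C'/A count some in-window IV-rtPA patients as untreated, so they do not fully measure what the first primary objective asks among overall AIS patients. This, and the fact that the arrival rule loses only patients with DTN under 60 min, follows from the plan's definitions.

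The growth of the loss across waves is conditional on similar arrival patterns and treatment decisions, and the sizes are illustrations under Step 3's assumptions. At a median DTN of 60 min they are 2.7-14.3% (3h row) and 1.1-7.9% (4.5h row), making a rise look modestly smaller.

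The documents do not support reading this as a concealed restriction, a flaw in C/B or C'/B', or a bias in the DTN outcomes. It is a worthwhile, inexpensive addition and does not threaten the study's main comparison.

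**What to change.** In Table 3.1, add for each window a row whose numerator is every group A patient given IV-rtPA within 3h (4.5h) of onset, whatever the arrival time or eligibility. Keep C/A and C'/A, relabelled to show that they cover patients who arrived by 2h (3.5h) and were eligible. Leave C/B, C'/B' and Tables 3.2.1 and 3.2.2 as they are, with no extra DTN rows.

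The SAP variable dictionary already lists hours from onset to arrival and from onset to tPA, so no new data are needed. The cost is two table rows and a footnote. The drawback is a second all-AIS figure whose numerator differs from that of the primary ratio. The footnote should say so, and state how patients with a missing treatment time or with added intra-arterial or experimental therapy are counted. If the redacted text already contains an unrestricted row, only the relabelling remains.
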